### **Statistical Procedures**

40 subjects will be recruited to account for a predicted 20% dropout rate in order to retain 32 subjects. For phase 1, the primary outcome is difference in food intake after 7 days of drug compared to placebo. Based on known acute changes in food intake after LOR a sample size of 24 subjects would be required using paired analysis (10). This sample size is more than adequate if CSF POMC is used as the primary outcome variable using a SD of 59 fmol/m (for overweight and obese subjects) to detect a 20% change in CSF POMC as has been reported for hypothalamic POMC in animals after treatment with 5-HT2cR agonists (23). However in order to use the outcomes of phase 1 to predict phase 2 wt loss, 40 subjects will be recruited to retain 32 and to achieve a range of wt loss as predicted by clinical trials (9). Food intake, including food energy and macronutrient consumption will be correlated with baseline POMC and AgRP levels. Differences in food intake at the placebo and LOR test meals will be correlated with changes in melanocortin peptide levels as well as with wt loss after 24 wks. Multiple regression modeling will be used to predict phase 2 wt loss in the LOR-treated participants from the within-subject difference between LOR and placebo test meal results and CSF POMC measurements from Phase 1. Bivariate Pearson correlation coefficients will be determined and stepwise multiple regression analyses will be performed to detect associations between POMC and AgRP and changes in levels following LOR and placebo with relevant variables: wt change, food intake, adiposity, leptin, sOB-R, insulin, HOMA-IR, gut hormones. Phase 1 is a double-blind trial with lorcaserin and placebo. After 10 subjects completed phase 1 the investigators were unblinded to the treatment of those 10 subjects in order to perform an interim analysis on the neuropeptide changes. We did detect a significant change in CSF POMC levels in the first 10 subjects but changes were not significant for other POMC derived peptide values. We would now like to unblind the next 10 subjects who have completed phase 1 in order to perform an interim analysis on the first 20 subjects as this may help with determining if we need additional POMC-derived study markers and optimization of assay conditions. The double blind will then continue for the subsequent study subjects.

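### Unblinded neuropeptide results from the first 20 phase 1 completers may guide marker and assay choices, with no rule protecting the final LOR-placebo neuropeptide comparisons

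*Combined protocol and SAP*

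**What the plan says.** All of this is in Statistical Procedures of the combined protocol and SAP.

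- **Primary outcome.** For phase 1, "the primary outcome is difference in food intake after 7 days of drug compared to placebo".
- **First look, already taken.** After 10 completers, "the investigators were unblinded to the treatment of those 10 subjects in order to perform an interim analysis on the neuropeptide changes". The result is reported: "We did detect a significant change in CSF POMC levels in the first 10 subjects". The remaining peptides derived from POMC showed no significant difference.
- **Second look, requested.** "We would now like to unblind the next 10 subjects who have completed phase 1". This gives a cumulative analysis of 20, justified because "this may help with determining if we need additional POMC-derived study markers and optimization of assay conditions".
- **Protection stated.** The double blind is to resume for subjects after these 20. The only other unblinding provision, in Data and Safety Monitoring, concerns medical emergencies.
- **Sample size.** Food intake gives 24. Of CSF POMC the text says only "This sample size is more than adequate if CSF POMC is used as the primary outcome variable". The recruitment figure serves the prediction of phase 2 weight loss: "40 subjects will be recruited to account for a predicted 20% dropout rate in order to retain 32 subjects".

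The section states no significance level and no multiplicity correction. It gives no rule for choosing or freezing a marker or assay version, and no role for the first 20 subjects in the final neuropeptide comparison.

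**The concern.** Results by treatment are the stated input to two decisions: whether to add POMC-derived markers and how to run the assays. The first look found a drug effect on one analyte and none on its relatives, which is a natural prompt to adjust the assays that showed nothing. If an assay version or marker is then retained because it separated drug from placebo better in the first 20, and those 20 are counted again in the final test, the same chance fluctuation is used twice. The nominal p-value then overstates the evidence, and a reader cannot tell how many versions were tried.

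What is exposed is the LOR-placebo comparison of neuropeptides. Study Purpose and Rationale treats showing that the drug activates POMC neurons as important, and Statistical Procedures considers a 20% change in CSF POMC. The blind in later subjects does not cover this, because the choice would already have been made on unblinded data.

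**Working it through.** **Inputs from the plan.** Recruited 40, dropout 20%, retained 40 × (1 − 0.20) = 32, which reproduces the plan's figure. Cumulative look at 10 + 10 = 20. At the final analysis the first 20 would be 20/32 = 62.5% of the retained subjects, or 20/40 = 50% if all are kept.

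**Assumptions, not in the plan.** Two-sided 0.05; paired t-test on within-subject differences; the first 20 pooled into the final test; k candidate versions with normal differences and common correlation ρ; the version with the largest difference at n=20 is kept and tested at N. Two rankings are considered: by absolute difference, and in the one expected direction.

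**Statistic.** t = mean(d) / (SD(d)/√N), rejected if |t| > t(0.975, N−1). Simulation under no drug effect, 200,000 trials per setting, Monte Carlo standard error about 0.05 percentage points.

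| False positives, % | ρ=0 | 0.5 | 0.8 | 0.9 | 0.95 |
|---|---|---|---|---|---|
| k=2, N=32, absolute | 9.0 | 8.3 | 7.2 | 6.6 | 6.2 |
| k=2, N=40, absolute | 8.2 | 7.8 | 7.0 | 6.4 | 5.9 |
| k=2, N=32, directional, total | 5.0 | 5.0 | 5.0 | 5.0 | 5.0 |
| k=2, N=32, directional, favourable tail (nominal 2.5) | 4.8 | 4.2 | 3.6 | 3.3 | 3.1 |
| k=3, N=32, absolute | 12.0 | 10.8 | 8.7 | 7.6 | 6.9 |
| k=3, N=32, directional, favourable tail (nominal 2.5) | 6.5 | 5.6 | 4.4 | 3.8 | 3.4 |

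Versions of one assay measure the same analyte in the same samples, so the right-hand columns are the relevant ones for assay choice. The left-hand columns fit distinct markers better.

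**What is not inflated.** A version fixed without treatment codes: 4.9-5.1%. A Pearson test of the selected marker against an independent weight loss: 4.9-5.1%.

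**Effect of Bonferroni, N=32.** Absolute ranking returns to 3.2-4.7% (k=2) or 2.4-4.4% (k=3), so it is conservative. The smallest observed difference reaching significance is t(1 − 0.025/k, 31)/√32:

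- k=1: 2.040/5.657 = 0.361 SD
- k=2: 2.356/5.657 = 0.416 SD
- k=3: 2.531/5.657 = 0.447 SD

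For a true difference of 0.5 SD the noncentrality is 0.5 × 5.657 = 2.83. Power against those critical values is about 78%, 68% and 62%.

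**The case against.** The strongest reply is that the harm needs a rule the plan does not contain. The text speaks of adding markers, not of keeping a winner, and a marker added without selection is not inflated. That stands, and the percentages above are therefore conditional. It is also true that the unblinded subjects had finished phase 1, so their meals and samples were collected under the blind, and that the blind continues for everyone after them. The highest rates need uncorrelated versions, which is implausible for one assay. None of this supplies what is missing, which is a statement separating the choice from the drug effect.

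A reader might infer more than the documents support:

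- **That the phase 1 primary is compromised.** Food intake is named as primary and is not described as part of either look.
- **That the weight-loss prediction is compromised.** Choosing a marker on its drug-placebo difference does not inflate its test against 24-week weight loss under the null.
- **That CSF POMC sizes the trial.** The 24 comes from food intake and the 40 from predicting phase 2 weight loss. CSF POMC is only remarked to be covered.
- **That repeated looks alone raise the error.** Declaring significance at any of unadjusted looks at 10, 20 and 32 would give about 11%, but the plan describes no early stopping and no final claim based on an interim result. A single final test of a marker and assay fixed beforehand keeps its 5%.
- **That CSF POMC will be promoted to primary after its favourable first look.** The plan does not say so, and switching on the n=10 result would give only 5.3-5.8% at N=32.

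**Conclusion.** The point holds as a minor one, confined to the non-primary LOR-placebo neuropeptide comparisons. The plan proposes to let treatment-unblinded results inform marker and assay choices, and it has no rule that keeps the drug effect out of those choices or accounts for it afterwards.

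If the better of two versions were kept on its drug effect at n=20, the two-sided error at N=32 would be about 6-9%, and about 6% where versions are highly correlated. With directional selection the total would stay about 5% and the favourable tail would be about 3-5% instead of 2.5%. These figures rest on an assumed 0.05 level, an assumed selection rule and pooling of the first 20. They illustrate what the silence allows and do not describe what the investigators intend.

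**What to change.** Amend Statistical Procedures in two places.

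1. **Assay conditions.** Optimise on treatment-blind criteria only: precision, recovery and detection limit, with both visits pooled. Settle the conditions before any further codes are released, and release no codes for this purpose. The order matters: if the second look came first, the same investigators would already have seen the drug effect.
2. **Markers and versions chosen or added after an unblinded look.** Report how many were tried and label their LOR-placebo comparisons exploratory. If a confirmatory claim is wanted, Bonferroni-correct over the number tried in the full sample.

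**Cost.** No extra subjects. The exploratory label costs no power but gives up a confirmatory claim for those markers. Bonferroni lowers power at N=32 for a true 0.5 SD difference by about 10 points (two versions) or 16 points (three), and over-corrects when versions are correlated. The food-intake primary loses nothing. Restricting the final test to later subjects would also hold the error near 5%, but it leaves 32 − 20 = 12 subjects. At a standardised difference of 0.597 (the size that 24 subjects detect with 80% power), power would fall from about 90% to about 47%, so I do not recommend it.

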### **Data and Safety Monitoring**

This study is considered to be of low risk to the participants but the risk is considered to be more than minimal risk as there is the potential risk as outlined above of post-dural puncture headache. Subjects will be monitored for any adverse effect related to taking lorcaserin at all study visits over the 24 week period. CBC and metabolic panels will be obtained at monthly intervals for the first 2 month and then every 2 months for the remainder of the study. It is exceedingly unlikely that excess adverse events will occur and require stopping the study. However this will be carefully monitored by Drs. [name] and [name] and the Safety Ofcer, [name]. Each subject is evaluated for any adverse events. An adverse event is dened as both an expected side effect that is of a serious nature, or an unexpected side effect/event regardless of severity. All events will be graded as to their attribution (unrelated to protocol, or possibly, probably, or denitely related to protocol). Any event that is reported to either the principal investigator or her designated research associates by the subject or medical staff caring for the subject and which meets the criteria will be documented as such. All adverse events will be graded as mild, moderate, or severe. Any severe and/or unanticipated adverse event will be reported within 24h to the Safety Ofcer and IRB. All adverse events will be reported to the Safety Ofcer every 6 months. All adverse events will be summarized annually and submitted to the IRB. Unblinding Procedure The subject's safety takes priority

over any other considerations in determining if the treatment assignment should be unblinded. In the event of a medical emergency in which knowledge of the treatment is critical to a subject's management, the investigator may break the blind for the participant.

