Subjects will be recruited for a 5-week crossover study with lorcaserin (LOR) and placebo followed by treatment with LOR or placebo for 24 weeks. **Phase 1:** Participants will be randomized to receive either LOR (10 mg bid) or placebo for 7 days followed by a 3 week washout period and will then be crossed over to receive 7 days of the other treatment (LOR or placebo). Thus each subject will be studied twice: once after receiving placebo and again after receiving lorcaserin. *Subjects will continue on a weight maintenance diet during this time to remain weight stable.* Salivary cortisol levels will be obtained at 0800h and at 2300h on days 2 and 6 of placebo and LOR. A 24h urine will be collected on day 6 of placebo and day 6 of LOR. On day 7 of both the placebo and LOR treatments, subjects will be studied in the clinical research center in the morning after an overnight fast. A lumbar puncture (spinal tap) will be performed and blood samples will be obtained. Subjects will then be fed a standardized breakfast (300 kcal). A laboratory test meal will be performed 4h later as described below. **Phase 2:** After completing the 7-day placebo and LOR studies, subjects will then be treated with LOR 10 mg bid (n= 40) for 24 weeks (Fig. 1). *Subjects will receive nutritional counseling to reduce their daily caloric intake to 600 kcal below their calculated caloric requirement and will be encourage to exercise moderately for 30 min daily.* Subjects will visit the clinic monthly during the 24 week study period for monitoring of vital signs and food counseling which will include review of food diaries. Salivary cortisol levels will be obtained the night before the monthly visits. Blood will be obtained at months 1, 2, 4 and 6 for safety monitoring and protein and hormone level analysis. At the end of the 24 week period subjects will be admitted to the GCRC for an LP followed by a fixed breakfast and a laboratory test meal 4h later. CSF will be tested for various proteins and hormones. Subjects will collect a 24h urine beginning the day before this final LP.

**Lumbar Puncture:** LP will be performed after an overnight fast by [name], Professor of Anesthesia and Director of Obstetrical Anesthesia, using a 25G Whitacre needle. 12 ml of CSF (approximately 2 teaspoons) will be removed at each LP.

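### The only timed monitoring rule covers lorcaserin effects in the 24-week phase; no scheduled adverse-event assessment is specified for the blinded crossover or for lumbar-puncture effects

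*Combined protocol and SAP*

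**What the plan says.** The Data and Safety Monitoring section explains why the study is above minimal risk: "there is the potential risk as outlined above of post-dural puncture headache". Its next sentence sets the monitoring rule: "Subjects will be monitored for any adverse effect related to taking lorcaserin at all study visits over the 24 week period". No other sentence in the section says when subjects are assessed for adverse effects. Blood counts and metabolic panels do have a schedule, but Study Design places the safety bloods within the 24-week phase (months 1, 2, 4 and 6).

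Three further provisions in the section carry no timing:
- Every subject is assessed for adverse events.
- Attribution is graded to the protocol as a whole.
- Events that subjects or medical staff report are documented if they meet the definition. That definition counts an expected side effect only when it is serious, and an unexpected one at any severity.

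Study Design gives the timeline. Phase 1 is a crossover of 7 days, a 3-week washout and 7 days: "Thus each subject will be studied twice: once after receiving placebo and again after receiving lorcaserin". For each day-7 visit it states "A lumbar puncture (spinal tap) will be performed and blood samples will be obtained". The 24-week phase follows, and then: "At the end of the 24 week period subjects will be admitted to the GCRC for an LP". No visit or contact after that admission is described.

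**The concern.** The timed rule and the stated risk do not match. The risk that sets the study's classification comes from a procedure, while the rule looks for effects of a drug. Most of the procedures, and each subject's first exposure to the drug, come before the rule's window opens.

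Two things are at stake. First, the plan relies on six-monthly reports to the Safety Officer and annual summaries to the IRB to show whether harms are accumulating. If puncture effects are not asked about on a schedule, those reports may under-count the main named risk. Second, Statistical Procedures describes Phase 1 as double-blind, and each subject takes both treatments in it. It is therefore the clearest setting for comparing event rates on drug and placebo within the same person, yet no scheduled event collection is specified for it.

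**Working it through.** **Inputs.** From Study Design: Phase 1 is 7 days + 3 weeks + 7 days; there is one lumbar puncture on day 7 of each treatment and one at the end of week 24. From Statistical Procedures: 40 recruited, 20% dropout, 32 retained.

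**The plan's own figures.**
- Phase 1 length: (7 + 21 + 7) / 7 = 5.0 weeks, matching the stated 5 weeks.
- Recruitment: 32 / (1 − 0.20) = 40, matching the stated 40.

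**Punctures against the monitoring window, per subject.** Two precede the 24-week period and one falls at its end: 2 of 3.

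**Totals, by when dropouts leave.**

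| Case | Phase 1 punctures | Week-24 punctures | Share before the window |
|---|---|---|---|
| No dropout | 40 × 2 = 80 | 40 | 80/120 = 66.7% |
| 8 leave before any puncture | 32 × 2 = 64 | 32 | 64/96 = 66.7% |
| 8 leave after both Phase 1 punctures | 40 × 2 = 80 | 32 | 80/112 = 71.4% |

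The range is 67% to 71%. The Scientific Abstract gives 60 subjects where the other sections give 40. That would change the totals but not the two-in-three count per subject.

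**Time in study.** Phase 1 is 5 of 5 + 24 = 29 weeks, or 17%, but it holds two of the three punctures.

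**Next described visit after each puncture.**
- First: the day-7 visit of the second crossover period, 21 + 7 = 28 days later.
- Second: the monthly visits of the 24-week phase.
- Third: none described.

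The first two punctures therefore have a later visit. For the visit after the first, no adverse-event enquiry is specified. For those after the second, the timed rule asks only about lorcaserin effects.

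**Would the definition record the event?** Post-dural puncture headache is named in advance, so it is an expected effect. Under the definition, an expected effect that is not serious does not qualify. A mild headache that a subject volunteers could therefore go undocumented, and widening the window alone would not change that.

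**The case against.** The strongest reply is that the section as a whole is wider than its one timed sentence. It says without limit of drug or phase that each subject is assessed for adverse events, and it grades attribution to the protocol, which includes the puncture. Its emergency unblinding clause also reaches Phase 1, the phase described as double-blind. This stands. A reader might infer that Phase 1 and the punctures go unmonitored, and the documents do not support that. What they lack is a stated time, method or visit for the wider assessment.

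Second, the headache risk is said to be outlined above, and that outline is not in the pages available for this review. It may describe follow-up after a puncture. So the absence of a later contact can be asserted only for the text reviewed.

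Third, the 67% to 71% counts punctures that precede the window, not punctures without any later visit. Only the week-24 puncture lacks one in the text. Subjects also stay for breakfast and a test meal 4 hours after it, so they are under observation for some hours after every puncture. This too stands. It does not help with a headache that begins after the subject goes home.

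Fourth, a reader might infer that Phase 1 is the only placebo-controlled part of the trial. The documents conflict. Study Design opens with "Subjects will be recruited for a 5-week crossover study with lorcaserin (LOR) and placebo followed by treatment with LOR or placebo for 24 weeks", and the Scientific Abstract has similar wording, but the Phase 2 description says "subjects will then be treated with LOR 10 mg bid (n= 40) for 24 weeks". The point here does not depend on how that is resolved.

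Finally, comparing adverse-event rates between drug and placebo is not a stated objective. That is true, and it makes the Phase 1 tabulation a secondary benefit. The case for asking about puncture effects rests on the plan's own risk statement.

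**Conclusion.** The point holds as a mismatch in scope. The one timed monitoring rule is restricted to lorcaserin effects in the 24-week phase. In the text reviewed, no scheduled adverse-event assessment is specified for the 5-week blinded crossover or directed at lumbar-puncture effects at any time. Two of three punctures per subject precede the rule's window: 80 of up to 120, or 67% to 71% depending on when dropouts leave. The third falls at the window's end with no later contact described.

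This rests on two assumptions: that the untimed general sentences do not imply a visit schedule set out elsewhere, and that the unavailable risk text does not already provide follow-up after a puncture. The documents give no headache rate, so the number of events that might go unrecorded cannot be estimated. Sample size, power and error rates are unaffected. The change is worth making because it corrects a stated rule at little cost.

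**What to change.** 1. Reword the monitoring sentence so that adverse events of any cause, drug or procedure, are actively asked about at every Phase 1 and Phase 2 visit.
2. Unless the risk section already provides it, add a short dated contact by existing staff after each lumbar puncture, including the one at week 24, recording headache (yes/no), onset and severity.
3. Reconcile the adverse-event definition with this, so that non-serious post-dural puncture headache is recorded although it is expected.
4. Tabulate Phase 1 events by treatment period, and puncture-related events with the number of punctures as denominator.

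The cost is protocol wording and up to three short calls per subject, at most 3 × 40 = 120 calls. No sample size or planned efficacy analysis changes.

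### Read literally, the adverse event definition leaves expected non-serious effects out of the six-monthly and annual safety reports

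*Combined protocol and SAP*

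**What the plan says.** All the relevant text is in the Data and Safety Monitoring section of the combined protocol and SAP.

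- **Definition.** An adverse event is "an expected side effect that is of a serious nature, or an unexpected side effect/event regardless of severity".
- **Documentation.** A reported event "which meets the criteria will be documented as such", where the criteria are those of the definition.
- **Attribution and grade.** "All events will be graded as to their attribution", and "All adverse events will be graded as mild, moderate, or severe".
- **Expedited reporting.** "Any severe and/or unanticipated adverse event will be reported within 24h" to the Safety Officer and the IRB.
- **Periodic reporting.** "All adverse events will be reported to the Safety Ofcer every 6 months" and "All adverse events will be summarized annually and submitted to the IRB".
- **Surveillance.** "Each subject is evaluated for any adverse events". The section also has subjects monitored at the 24-week-phase visits for adverse effects of lorcaserin, with no limit by expectedness or seriousness.

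The section names post-dural puncture headache as the reason the study is rated above minimal risk. It refers back to a risk description that is not in the text available for this review.

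**The concern.** Periodic safety reports are where the ordinary side effects of a drug or procedure should become visible. These effects are foreseen and individually minor, so nobody would expedite them. This definition admits a foreseen effect only if it is serious. The documentation rule and both periodic reports then depend on the defined term, so the restriction carries through to what the Safety Officer and the IRB receive.

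What is at stake is the completeness of routine safety reporting. A non-serious post-dural puncture headache illustrates the problem, unless the risk description not seen here has its own recording rule for it. A known, non-serious effect of lorcaserin would be treated the same way. The restriction also fits poorly with the section's unrestricted monitoring for drug effects: staff are asked to look for more than they are required to report.

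**Working it through.** No planned figure is involved, so the check is to follow each type of event through the section's own rules.

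**Step 1: cross expectedness with seriousness.**

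| Type of event | Meets the definition? | Must be documented as an adverse event? | Enters the six-monthly and annual reports? |
|---|---|---|---|
| Expected, serious | Yes, first limb | Yes | Yes |
| Unexpected, serious | Yes, second limb | Yes | Yes |
| Unexpected, non-serious | Yes, second limb | Yes | Yes |
| Expected, non-serious | No | No | Not required |

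One cell of four is left out. The definition joins its two limbs with an awkward both/or construction. Reading it as requiring both limbs would narrow the definition further, so neither reading brings in the fourth cell.

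**Step 2: see whether another sentence closes the gap.**

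- The attribution sentence refers to all events, not all adverse events. It suggests that other events are recorded, but it creates no duty to report them.
- The sentence on evaluating each subject uses the restricted term, so it adds nothing to it.
- The existence of a mild grade proves nothing, because unexpected mild events can fill it.
- The monitoring sentence covers lorcaserin effects generally but attaches no recording or reporting duty.

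No other section of the available text gives a wider definition.

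**Step 3: locate the edge of the gap.** The available text does not define serious or say how it differs from the grade severe.

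- If serious means graded severe, the omitted events are the expected mild and expected moderate ones.
- If serious is separate from grade, expected non-serious events of every grade are omitted.

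The size of the gap depends on this choice; its existence does not.

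**Step 4: see what a wider definition does to the 24-hour rule.** That rule applies to a severe and/or unanticipated adverse event, so it too uses the defined term. If serious is separate from grade and the definition is widened with nothing else changed, expected, severe, non-serious events would newly fall under 24-hour reporting. If serious means severe, nothing new is added. A change of definition therefore has to state the 24-hour scope explicitly.

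**Step 5: see how far the trial has run.** The Statistical Procedures section says that 10 subjects had completed phase 1 at the first unblinding and that the next 10 have also completed it: 10 + 10 = at least 20. A new definition cannot govern how their phase 1 events were captured.

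**The case against.** The strongest defence is that the label is narrower than the practice. The attribution sentence follows directly on the definition and covers all events, and an event graded for attribution is plausibly written down. Visits look for any lorcaserin effect. Expected serious and all unexpected events reach the Safety Officer and the IRB, and the Statistical Procedures section plans no adverse event analysis that incomplete capture could distort. Much of this stands: it limits the consequence and makes wider capture the likely intention. It does not put expected non-serious effects into either periodic report, because both are tied to the defined term.

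A reader might infer three stronger things that the documents do not support.

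- **That the periodic reports add almost nothing to the 24-hour reports.** This requires unanticipated to mean unexpected, and the section uses both words without equating them. Suppose serious means severe. Then 2 levels of expectedness × 3 grades = 6 classes, of which 3 unexpected + 1 expected severe = 4 are adverse events. The 24-hour rule covers 4 of these if the two words are equal, and only the 2 severe classes if unanticipated adds nothing beyond severe events. The periodic reports then add 4 − 4 = 0 to 4 − 2 = 2 classes. If serious is separate from grade, there are 2 × 2 × 3 = 12 classes, 6 + 3 = 9 are adverse events, and the 24-hour rule covers 7 to 3, so the periodic reports add 2 to 6. Collating individual reports is useful in any case.
- **That the watch for an excess of adverse events rests on an incomplete total.** The section names no total, rate or threshold. It says only that the investigators and the Safety Officer will monitor carefully.
- **That the number of lumbar punctures measures the loss.** Punctures are procedures, not omitted events.

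**Conclusion.** The concern holds as a defect of wording with a practical consequence: a site that followed the section exactly could leave expected non-serious effects out of both periodic reports. This is a stated rule that yields incomplete reporting, not simply missing detail, and it conflicts with the section's own broader monitoring.

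Its size is one cell of the four in the cross-classification. The number of events cannot be estimated, because the documents give no event rates. The conclusion rests on a literal reading and on the available text; staff may in practice record more than the wording demands. The headache example, and any statement of which lorcaserin effects count as expected, depend on risk text not seen here, but the gap in the definition does not. The change is worth making because it is cheap, not because a safety signal is known to have been missed.

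**What to change.** Going forward, for recording and for the six-monthly and annual reports, define an adverse event as any untoward occurrence during study participation, expected or not and of any severity, recorded with its grade and attribution. In the same amendment:

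- state how serious differs from severe;
- say that the events covered by 24-hour reporting do not change;
- note the date from which the new definition applies.

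The cost is slightly more recording, with no new visit or procedure. The trial would also carry two capture definitions, since at least 20 subjects have already completed phase 1. Safety summaries should therefore show which events were collected before and after the change, and the two periods should not be compared as if capture had been the same.
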